As explained above, the data collection will be carried out through FGDs and KIIs. The FGDs will be conducted with the group of participants consisting of 10-15 people and the duration of each FGD will be 60 to 90 minutes. The FGD participants will be a homogenous group with respect to age, gender, socio-economic status, etc. Each KII will be conducted for the duration of 30 to 45 minutes. Separate interview guides will be developed for FGDs and KIIs with predefined domains including understanding about gender roles, concept of masculinity, violence and women empowerment. The interview guides will be developed by reviewing the available literature and mutual consultation with experts within the team. All the interviews will be tape recorded after taking informant consent from the participants. The data collection will continue till the level of saturation is achieved. All the interviews and discussions will be conducted in the local language, convenient to the participants.

Data Management

Transcription and Translation

A thorough meeting will be conducted at the end of every interview and discussion sessions. The audio tapes and field notes will be properly labeled with the date, time, name of the group and participants. The moderator and the note taker will examine all the field notes. After the discussion, further probes and additional questions may be added to the interview guide for next interview or discussion, if required. All the recorded interviews will be transcribed to Sindhi/Urdu followed by

translation to English language. After the translation, the moderator and translator will check the translated script against the recorded tapes for accuracy and consistency.

Data Analysis

Analysis of the qualitative data will be conducted using Braun and Clark's thematic analysis (Braun & Clarke, 2006). The researchers will begin by familiarizing with the data, generating codes, searching, reviewing and naming themes. Relevant categories will be picked from the transcribed data and linked to the different themes. All disagreements will be discussed and consensus will be reached on the overall analysis. All the transcripts will be reviewed again in the end to make sure that the necessary information had been captured.

Phase 2: Cluster Randomized Control Trial

In the second phase, a Cluster Randomized Control Trial will be performed for 2 years.

Inclusion and Exclusion Criteria

The couples will be recruited from the list of women who are receiving BISP-CT and meet the eligibility criteria of: adult married women who: receive BISP-CT, have one child of at least 18 months and have no family migration plan for next 2 years.

The couple in which either of the partners has gross mental impairment, physically challenged or bedridden, will be excluded.

Sample Size

There will be three groups for cRCT. The first group will receive LSB to BISP-CT beneficiaries and their husbands. The second group will receive LSB only to women receiving BISP-CT. The third group will be the control arm who will receive BISP-CT only. Assuming an average cluster size of at least 25 couples, with the baseline prevalence of depression 60% and expected reduction of 20% in intervention arm, 9 clusters per arm would be needed over a period of two years. There are three arms and 9 clusters in each arm so a total of 675 couples (225 in each arm, 25 in each cluster). By accounting for the attrition rate of 25%, a minimal of 846 couples (282 per arm) would be needed.

Sampling Strategy

During the first level of assessment, out of the four Tehsils in District Thatta, Tehsil Mirpur Sakro will be finalized for the intervention, since Tehsil Thatta is saturated with other NGOs/Projects, Tehsil Ghorabari and Tehsil Ketu Bunder are difficult to manage administratively, being far away and coastal areas. At the second level of assessment in Tehsil Mirpur Sakro, the UCs will be assessed based on the demographic characteristics, infrastructure, health facilities, accessibility and women mobility. The UCs being administratively hard to reach i.e. lack proper infrastructure (roads), saturated with other projects, being close to city with urban settlements, will be excluded. Three UCs i.e. Gharo, Gujjo and Chowbandi will be identified as the potential sites for the intervention. Within the UCs, Deh/Village is the smallest unit, but since there is no clear demarcation between Dehs, therefore village or a group of small villages will be considered as a cluster. The clusters will be created by grouping small villages with respect to geographic boundaries, ethnic cast and number of households. Each cluster will have sufficient number of households to achieve the targeted cluster size. The large geographically separated villages will be considered independent clusters. The mapping of clusters will be done in a way to maximally avoid contamination. A minimum of 27 clusters will be selected randomly from a sufficient pool of clusters i.e. 9 from each arm keeping same number of clusters per arm in each UC. At the third level of assessment, the clusters of the selected UCs will be randomly assigned to three arms. The clusters will be selected for randomization based on the assumptions, i.e. having sufficient number of BISP beneficiary households meeting our eligibility criteria, the intervention and control clusters will not be in close proximity thus chances of contamination are minimal.

Operational Plan

The implementation of the manualized LSB curriculum will be delivered through 10-12 sessions (10 for couples, 2 for family including mother-in-law, supporter or head of the household), one session per week for each cohort of 282 couples. Therefore, for three cohorts, a total of 846 couples, will require nine months. There will be 12 LSB teachers (8 females, 4 males) working in six pairs for six groups (4 women, 2 men) for the entire year. The purpose is to ensure high quality staff, optimum delivery of the intervention between the cohorts, and proper fidelity monitoring. Regarding the data collection plan, the data collection points are pre-intervention (baseline) and post-intervention (end-line, five months). The schematic illustration is mentioned below in figure 4.

[figure not shown]
Safety protocols amid COVID 19

Capacity building of the research team will be carried out, where a comprehensive COVID-19 awareness training will be offered to the field team. The field preparations will include; adequate supply and use of PPEs (face masks, sanitizers), information communication material (in local language) to be used in field office and community settings. Furthermore, the team will work closely with the DC office Thatta to obtain the list of nearby health facilities assigned by the provincial government to provide COVID-19 screening, testing, isolation/quarantine, treatment/referral in the study area. This exercise will ensure the safety and wellbeing of staff and community participants, before the actual delivery of LSB intervention in the study area.

Moreover, to ensure the wellness of field staff, an orientation regarding the use of CoronaCheck; a new mobile app that enables them to easily and safely evaluate symptoms with an in-home screening tool and understand the next steps they need to take to look after themselves, will be provided. The app allows the staff to understand their symptoms, identify whether they may have contracted COVID-19 and seek help in a timely manner. It also helps the staff to identify potential coronavirus carriers and limit their risk of transmission. It will be assured that, the staff should use the app on daily basis as they come to office and contact AKU employee health service for initial screening and if needed testing.

In community, the participants will be provided awareness sessions on novel corona virus and measure to keep the surroundings safe and healthy. Furthermore, they will be provided PPEs (face masks and sanitizers). In order to maintain the safety and wellness of both LSB teachers and participants, social distancing and frequent hand washing will be ensured during each session. Large groups sessions will be avoided and the number of participants will be restricted between 5-6 per session. Two sessions per day will be conducted instead of one by each pair of LSB teacher, to train 10-12 participants as per the plan of delivery.

Figure 4. Schematic illustration

Process Outcome Measures

Outcome measures for men and women receiving LSB training are the same. Process indicators include number of couples trained, number of sessions attended by couples, and number of follow-up assessments completed.

Data Management

Pre-testing

The translated versions of the questionnaires will be pre-tested by being administered to approximately 10% of the sample size in a district similar to the selected district. The completed questionnaires will be sent for data entry so that the psychometric properties of the scales will be checked. Any difficulties in translation, comprehension or item performance will be resolved by team discussion after this and final changes made to the questionnaire.

Tracking Participants

The study dataset will be a closed cohort and so it is important to track participants to determine cause of any loss to follow up and also to be able to connect interviews completed at different rounds. In order to do this we will complete an enrolment form for each couple in the study. These will be completed on paper and will be stored under lock and key at Aga Khan University. Each tracking form will include a randomly generated 6 digit number which will be that couple's

research ID and initials. In electronic data the couples will only be identified by research ID and initials which cannot be electronically linked to their name.

The tracking form will include the following information:

- Allocated ID
- Name
- Union Council, Tehsil, District
- Address
- Contact numbers
- CNIC numbers of couple

Assessment Tools

The outcomes will be assessed through validated instruments including Patient Health Questionnaire (PHQ-9), The Revised Conflict Tactics Scale, General Self-Efficacy Scale, Resilience Scale, Economic Solvency, Gender Equitable Attitude Scale and Six-item Food Security Questionnaire. Pilot testing will be done followed by modifications in the tools, if and where required.

Demography

Demographic profile will be used to assess the overall information about the family, its economic and educational status. This form was designed and utilized in the Global Network Research Unit (GNRU) project on perinatal infections and pregnancy outcomes which was funded by National Institute of Health (NIH), with AKU and University of Alabama as partners and other AKU funded researches (Karamaliani et al., 2009). This demographic profile form includes two sections:

Section A: Demographic profile: age, education, language, number of family members, number of married or unmarried and previous pregnancies and number of children.

Section B: Socio-economic Status: number of people actively working including type of work, timings and utilization, type of living with accessories and water drinking.

Section C: Economic Solvency: Financial assistance received other than BISP, financial assistance received for child support and cash assistance received from other people.

General Self-Efficacy Scale (GSE-10)

This 10-item instrument was created to assess a general sense of perceived self-efficacy with the aim to predict coping and adaptation after stressful life events (Schwarzer, 1995). Responses to each item are made on a 4-point scale: 1=Not at all true, 2=Hardly true, 3=moderately true, 4=exactly true. The possible range of scores is 10 to 40. In samples from 23 countries, Cronbach's alphas ranged from 0.76 to 0.90, with the majority in the high 0.80s. For the GSE, the total score ranges between 10 and 40, with a higher score indicating more self-efficacy (Schwarzer, 1995). For this study, the Urdu adaptation of the GSE tool, developed by Tabassum, Rehman, Schwarzer, and Jerusalem was used (Tabassum et al., 2003).

The Revised Conflict Tactics Scale (CTS2S-20)

The revised conflict tactics scale consists of 20-item and is self-administered. The scale includes items regarding Negotiation (1-4), Psychological aggression (5-8), Physical assault (9-12), Sexual coercion (13-16) and Injury (17-20). The scoring criteria consists of a scale from 1-8, 1-6 indicates the frequency of conflict happened in the past year ranging from once to more than 20 times. 7 indicates conflict happened not in the past year but happened before that. If it never happened, 8 will be marked (Douglas & Straus, 2004). There are many ways to score the CTS: Respondents who reported being a victim of or perpetrating an item or items (Prevalence). The number of times an item occurred in the past year (Frequency). Classifying each case into three categories: none, minor only, or severe (severity level). Classifying each case as respondent only, partner only, or both (mutuality types). For this study, Sindhi translated version will be used after pre-testing.

Patient Health Questionnaire (PHQ-9)

The Patient Health Questionnaire (PHQ) is a self-administered instrument for common mental disorders. The PHQ-9 is the depression module, which scores each of the 9 DSM-IV criteria as "0" (not at all) to "3" (nearly every day). It is used to monitor the severity of depression and response to treatment. It can be used to make a tentative diagnosis of depression in at-risk population (Kroenke, Spitzer, & Williams, (2001). For this study, the Urdu adaptation of the PHQ-9 tool will be used (Ahmad et al., 2018). This tool has been translated into Sindhi language and will be used in this study. PHQ-9 total score for the nine items ranges from 0 to 27. Scores of 5,

10, 15, and 20 represent cut points for mild, moderate, moderately severe and severe depression, respectively.

The Resilience Scale (RS-14)

We will use Wagnild's resilience scale for our study. This tool has been validated in Urdu in Pakistani context. This resilience scale comprised of five core characteristics of resilience that include: purposeful life, perseverance, equanimity, self-reliance and existential loneliness. It comprised of validated 14 items with 7-point Likert scale to rate the individual's evaluation ranging from 1 (Strongly Disagree) to 7 (Strongly Agree) (Shehzad et al. 2015). Item scores are summed to yield a total score ranging from 14 to 98, with higher scores suggestive of greater perceived resilience categorized as very low (14-56), low (57-64), on the low end (65-73), moderate (74-81), moderately high (82-90), and high (91-98).

Gender Equitable Attitude Scale (GEAS-21)

The Gender Equitable Attitude Scale is a 21 item scale with Likert scale ranging from 4 (strongly agree) to 1 (strongly disagree). It has been adapted from 34-item original "The Gender-Equitable Men Scale (GEM Scale)" and 13-item "Gender Equitable Men Scale" adapted in the context of Pakistan. This scale has been tested by Pak-IMAGES study by Promundo and Men's HUMQADAM program by Rozan (Ashfaq et al., 2018). Factor analyses support two subscales, and the scale is internally consistent ($\alpha = .81$) (Pulerwitz & Barker, 2008). The total score ranges from 21-84, where higher score shows more gender equitable attitudes.

Six-item Food Security Questionnaire (FSQ-6)

A six-item food security questionnaire (FSQ) will be used to assess the food insecurity. The scale is valid, reliable and sensitive screening tool of food insecurity in people. One study had found that a strong correlation between the two-item and six-item FSQ ($\rho: 0.895$; 95% CI 0.821, 0.940; $P, 0 < 0001$). Cronbach's α coefficient was found to be 0.94 and 0.90 for the two-item and six-item FSQ, respectively. FSQ yielded a sensitivity of 100% (95% CI 75, 100) and a specificity of 78% (95% CI 61, 90). The negative predictive value was found to be 100% (95% CI 88, 100) (Young, et.al 2009). The total score ranges between 0-6, where score 0-1 shows high or marginal food security, score 2-4 shows low food security, score 5-6 shows very low food security.

Data Analysis

To avoid possible human error of missed or incorrect entries, the entered data will be cross checked initially by data coordinator, and discussed with research team and principal investigators, if required. All the data will be double entered in Excel, followed by congruence check and cleaning. It will be imported to STATA version 12.1 for the analysis, after cleaning.

Descriptive Statistics: Descriptive statistical analysis will be run to look at the distribution of variables of interest and for outcome variables. Mean and standard deviation will be calculated for continuous variables, proportions will be calculated for the categorical variables.

Logistic regression will be used to assess the effect of LSB with maternal depression and other outcomes. All variables meeting the criteria will be used for building the final model. The variable found most significant in the univariate analysis will be subsequently added first and the next significant variable one after the other. Variables found statistically non-significant (>0.05), biologically not meaningful will be removed from the model. Multivariate logistic regression will be carried out to reach to the most parsimonious model.

Communication Plan and Stakeholder Management

The project team will involve stakeholders at multiple levels. At national, coordination with BISP office in Islamabad and other relevant programs on maternal and child health will be carried out to sensitize them about the study scope and the outcomes and their implications on policy. Study team will meet regularly in coordination with Umeed-e-Nau program management over the study period and will discuss the project implementation.

Local stakeholders will include the BISP offices in Sindh province. Regular coordination is needed with the provincial office Local Health Department in the study will also be presented the results. Biannual meetings will be set with local stakeholders to share research progress and milestones.

Monitoring and Evaluation Plan

The primary responsibility for monitoring the fidelity of the intervention delivery will rest with Aga Khan University and they will be required to ensure that a log sheet is kept recording the trainings conducted by faculty of AKU to train LSB teachers and number of couples who attended the training. This information will be reported quarterly to Principal Investigators. The information

will be compared to the planned intervention delivery schedule and deviations will be flagged and fed back to the project management team.

The research team will have responsibility for spot checks on the fidelity logs and field visits to ensure accurate, timely and smooth data collection and the LSB intervention delivery. The field coordinators will visit each intervention site independently for the monitoring of data collection and LSB intervention.

Project Management Structure and Organization

The overall responsibility for the study is on PI, component lead and co-lead and Co-PIs from the Aga Khan University School of Nursing and Midwifery, Psychiatry and Community Health Sciences department and they will have final scientific responsibility for the study including the research conduct, reporting of main outcomes, stakeholder relations and dissemination of findings. They will be supported in this role by technical advisor [name] of Texas Woman University. The project is multidisciplinary and will draw on expertise from a range of faculty members from other disciplines at Aga Khan University.

Technical and Financial Reporting

This team will report technically and financially to PI and Co-PI of Umeed-e-Nau (UeN) at COE-WCH, AKU and the funding agency.

Ethical Considerations

Ethical approval will be obtained for the present study from Ethics Review Committee (ERC) of Aga Khan University (AKU) Karachi. Permission for data collection will be taken from the concerned stakeholders. Study related material will be explained verbally and a brief description of study will also be provided in the consent form. It is also clearly explained in the consent form that there is no benefits or potential risk attached with the study. Furthermore, the members were given the right to withdraw at any stage of the study. Keeping in view the comfort level of participants the qualitative data collection (FGDs & KIIs) will be carried out in local languages. For Sindh the guides will be used in Sindhi language while for Khyber Pakhtunkhwa (KPK) the guides will be used and facilitated in Pashtu language. However, participants from Rahim Yar Khan and Labella will mainly be facilitated using Urdu version of interview guides will be used.

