Since men are frequently neglected in global health programs to improve maternal and child health, the BISP-CT plus LSB proposal for "couples" is an innovative strategy to test the involvement of men towards better maternal and child health. The extent of major maternal health deficits in Pakistan cannot be stressed enough; therefore, involving men is the new initiative which is being tested in this project. Previously mixed results were obtained in terms of reducing poverty and violence against women when BISP-CT & LSB were administered specifically to women only. Through the addition of men, the impact of LSB is proposed to be enhanced. Furthermore, the proposed study not only measures women empowerment alone but also couples' empowerment through the interventions mentioned above. The purpose is to improve maternal and child health by empowering women through LSB training to BISP beneficiary married couples.

Problem Statement

Women in Pakistan are deprived of basic human rights of education, health and economic independence. Women remain dependent on their husbands, financially and socially.

Studies conducted in other part of the world have supported CT and LSB to reduce poverty, depression and violence. Recently, the negative consequences of maternal depression on children have also been well documented.

Situational Analysis

The current situation of women in Pakistan due to financial dependence and poor life skills, as described above, makes the role of our research more imperative in combating this issue through innovative interventions.

More specifically, the scope of this project is to improve maternal mental health by decreasing depression, empowering women economically and psychosocially so that they can prevent their victimization from violence and improve their health and family. Since children brought up in a healthy environment will grow up to build stronger families and hence the vicious cycle of continuing violence can be interrupted and stopped.

Therefore there is a need to test the interventions related to financial enhancement with LSB training to decrease maternal morbidity (depression), domestic violence, increase women financial empowerment, maternal and child health and nutrition.

Hypothesis

Introduction of LSB to BISP-CT beneficiaries in couples will reduce domestic violence and depression in married women of reproductive age by 20% and improve women empowerment by 20%.

Aim and Objective

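### The enrolment target of 846 couples (282 per arm) is said to allow for 25% attrition but covers only about 20%

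*Protocol*

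**What the plan says.** The Sample Size section (Phase 2) builds the target in three steps, and the Executive Summary repeats them under Sample Size Estimation.

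- Cluster size: "Assuming an average cluster size of at least 25 couples".
- Number of clusters and couples: "There are three arms and 9 clusters in each arm", which gives "a total of 675 couples (225 in each arm, 25 in each cluster".
- Allowance for loss: "By accounting for the attrition rate of 25%, a minimal of 846 couples (282 per arm) would be needed".

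The Operational Plan then schedules delivery on the enlarged figures: "one session per week for each cohort of 282 couples. Therefore, for three cohorts, a total of 846 couples, will require nine months".

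The protocol shows no formula for the step from 225 to 282. It gives no second attrition rate and no other completer target from which 282 could have come.

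**The concern.** A sample size is enlarged for attrition so that the required number remains after the losses. Here the required number is 225 per arm and the anticipated loss is 25%, so the enrolled number should be at least 225 when multiplied by 0.75. The figure 282 fails that test. It looks like the common slip of adding 25% to the required number instead of dividing that number by the fraction retained.

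At stake is whether the stated enrolment minimum delivers the number of couples that the design says it needs. A reader who takes the sentence at face value would believe that the trial could lose a quarter of its couples and still have 25 per cluster to analyse.

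**Working it through.** **Inputs, all from the Sample Size section:** 3 arms; 9 clusters per arm; 25 couples per cluster; 225 per arm and 675 in total before attrition; attrition 25%; stated target 282 per arm and 846 in total.

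**1. Reproducing the stated figure.** 225 × (1 + 0.25) = 281.25, rounded up to 282; 3 × 282 = 846. Both figures match exactly. Rounding up within clusters does not give 846: 25 × 1.25 = 31.25, rounded up to 32, and 32 × 27 = 864.

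**2. What remains after a 25% loss from the stated target.**

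- Per arm: 282 × 0.75 = 211.5, against 225 required (13.5 short).
- Total: 846 × 0.75 = 634.5, against 675 required (40.5 short; 40.5/675 = 6.0%).
- Per cluster, on average: 211.5/9 = 23.5, against 25 required.

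**3. Attrition that 846 does cover.** 1 − 225/282 = 0.202, or 20.2%.

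**4. Enrolment that would cover 25%.** 225/(1 − 0.25) = 300 per arm, 900 in total. This is 900 − 846 = 54 more couples (18 per arm, 2 per cluster). If every single cluster must keep 25, then 25/0.75 = 33.3, rounded up to 34 per cluster: 306 per arm and 918 in total.

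**5. Effect on power.** The protocol states no significance level, power or intracluster correlation (ICC), so these are assumptions: a two-sided 5% test, a range of ICCs, and a fall from 60% to 40%. With m completers per cluster, the effective number per arm is

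n = 9m / [1 + (m − 1) × ICC],

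and, with p̄ = (p₁ + p₂)/2,

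power = Φ{ [ |p₁ − p₂| √n − 1.96 √(2p̄(1 − p̄)) ] / √(p₁(1 − p₁) + p₂(1 − p₂)) }.

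Example at ICC 0.05: m = 25 gives n = 225/2.2 = 102.3 and power 82.1%; m = 23.5 gives n = 211.5/2.125 = 99.5 and power 81.0%.

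| ICC | n, m = 25 | Power | n, m = 23.5 | Power | Loss (points, before rounding) |
|---|---|---|---|---|---|
| 0 | 225.0 | 99.0% | 211.5 | 98.6% | 0.4 |
| 0.03 | 130.8 | 90.3% | 126.3 | 89.3% | 1.0 |
| 0.05 | 102.3 | 82.1% | 99.5 | 81.0% | 1.0 |
| 0.10 | 66.2 | 63.6% | 65.1 | 62.9% | 0.7 |

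The protocol does not say whether the 20% reduction is absolute or relative. If it were relative (60% to 48%), the same formula gives 72.5% falling to 69.8% at ICC 0, and 40.5% falling to 39.6% at ICC 0.05. The loss would then be up to 2.7 points, from a lower starting level.

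**The case against.** The strongest reply is that the slip hardly matters. The number of clusters, which chiefly drives power in a cluster trial, does not change, and the power lost is about a point. The protocol also words its targets as floors: 846 is a minimum, 25 per cluster is a minimum, and the Sampling Strategy sets 27 clusters as a minimum. Nothing prevents the team from enrolling more. This is right about the size of the consequence, and it limits how much weight the point deserves. It does not rescue the sentence: a minimum said to account for 25% attrition should do so, and the Operational Plan schedules exactly 282 and 846.

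A second reply is that multiplication by 1.25 is inferred, since no formula is shown. That is fair. The exact match makes it very likely, but the shortfall in step 2 holds however 282 was obtained.

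A third is that the power figures use a normal approximation with only 9 clusters per arm. With a t reference on 16 degrees of freedom and unpooled variance, power at ICC 0.05 would be 78.2% falling to 77.1%. The levels are lower, but the difference is still about one point, so the conclusion is unchanged.

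It could also be said that 225 is an enrolled number and not a completer number. The text itself enlarges 225 for attrition, so 225 can only be the number needed after loss.

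**Conclusion.** The point holds. By the protocol's own figures, 846 couples cover 20.2% attrition, not 25%. At 25% attrition the trial would finish with 211.5 couples per arm, 6% below its stated requirement. This part needs no outside assumption.

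The consequence for power is small: about one percentage point at most for 60% against 40%, given the assumed two-sided 5% test and ICCs from 0 to 0.10. It is a clear arithmetic error in the sample-size justification that should be corrected. It does not threaten the design.

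**What to change.** Keep 846 and correct the statement about it. In the Executive Summary (Sample Size Estimation) and in the Sample Size section, say that 846 couples (282 per arm) preserve 225 per arm if attrition does not exceed about 20%, and that a 25% loss would leave about 211 per arm, or 23.5 per cluster on average. This changes wording only; the Operational Plan figures stand.

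If the sponsor prefers to keep a true 25% allowance, the target becomes 300 per arm and 900 in total (918 if each cluster must individually keep 25). The 900 option costs 54 more couples, and 282 and 846 must then be changed in the Executive Summary, the Sample Size section and the Operational Plan. Given the small gain in power, the wording change is enough.

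While that text is open, a few words stating whether the 20% reduction is in percentage points or relative would spare readers from having to infer it.

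### Domestic violence is scored over the past year at a single five-month end-line; if end-line is timed per cohort, part of that year precedes the first session and weakens a true effect

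*Protocol*

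**What the plan says.** The protocol lists domestic violence among its primary outcomes and hypothesises a 20% reduction (Hypothesis), without saying whether this is relative or absolute.

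Under Assessment Tools, the Revised Conflict Tactics Scale is coded so that "1-6 indicates the frequency of conflict happened in the past year ranging from once to more than 20 times", while "7 indicates conflict happened not in the past year but happened before that". On the choice of score it says only that "There are many ways to score the CTS" and lists prevalence, frequency, severity and mutuality. Data Analysis names logistic regression, which points to a binary score.

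On timing, the Operational Plan states that "the data collection points are pre-intervention (baseline) and post-intervention (end-line, five months". The Executive Summary places end-line after delivery but describes it in brackets as five months of intervention. Sessions run "one session per week for each cohort of 282 couples", with 10-12 sessions, and "for three cohorts, a total of 846 couples, will require nine months". No shorter or re-anchored recall period is stated for end-line.

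**The concern.** An end-line answer given a few months after the first session, but covering twelve months, includes acts from before the couple had received any training. Those acts are the same in expectation in every arm, so they fill the count without adding contrast. Once an act is coded as past-year, no later analysis can date it, so this is fixed by the questionnaire and cannot be repaired in a statistical analysis plan. At stake is the interpretation of a null result: it could reflect the recall window and not the intervention.

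**Working it through.** **Plan's own figures.** There is no sample-size calculation for violence. The planned 225 per arm (225 × 1.25 = 281.25, taken as 282; × 3 = 846) comes from depression prevalence, so there is no violence figure to reproduce.

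**Pre-start months in the window.** Inputs: 12-month recall; end-line at five months; 10-12 weekly sessions; 1 month = 4.348 weeks, so the course lasts 2.30-2.76 months.
- Five months from course start: 12 − 5 = 7.0 pre-start months.
- Five months after 10 sessions: 12 − 7.30 = 4.70.
- Five months after 12 sessions: 12 − 7.76 = 4.24.
- One common end-line five months after nine months of delivery (month 14), cohort starts assumed at 0, 3 and 6: elapsed 14, 11 and 8 months, so 0, 1 and 4.

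**Fall that shows in a past-year count**, with even recall and full effect from the first session: 20% × post-start months / 12.
- From start: 20 × 5/12 = 8.3%.
- After course: 20 × 7.30/12 = 12.2%; 20 × 7.76/12 = 12.9%.
- Common date: 20 × (12 + 11 + 8)/36 = 17.2%.

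**Sample needed for frequency, past-year against since-start window.** Assumptions: baseline past-year score taken just before start and used as covariate; rate × 0.8 after start; Poisson acts at annual rate μ. Let f = post-start months / 12. The expected difference is 0.2μf under either window, so the ratio of sample sizes is the ratio of residual variances summed over the two arms.
- Past-year: μ[2 − 0.2f − 2(1 − f)²]. The last term is the part explained by the overlap with the baseline year.
- Since-start: 1.8μf.
- f = 5/12: 1.236/0.750 = 1.65.
- f = 7.30/12: 1.572/1.095 = 1.44.
- f = 7.76/12: 1.621/1.164 = 1.39.

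Letting rates vary between women (gamma, shapes 1 and 0.3, calibrated to 40% past-year prevalence) gives 1.56 and 1.49 from start, 1.36 and 1.30 at 7.30 months, and 1.32 and 1.26 at 7.76 months.

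**Any-act prevalence**, same model, with the rate cut so that since-start prevalence falls by 20%: 2.15-3.9 times from start and 1.6-2.4 times after course.

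**Does the change give enough power?** For frequency in the Poisson case at 7.30 months, μ = −ln(0.6) = 0.511 and the difference is 0.2 × 0.511 × 0.608 = 0.0622. With (1.96 + 0.84)² ≈ 7.85, n per arm is 7.85 × 0.511 × 1.572 / 0.0622² ≈ 1,631 with the past-year window. With the since-start window (1.095 in place of 1.572) it is about 1,137. For prevalence, across both timings, the figures are 1,145-3,350 and 519-1,520. All exceed 225, before clustering.

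**Sensitivity to onset** (end-line after course, frequency). Compare a five-month window with the past-year window.
- Effect from the first session (7.30 months, Poisson): past-year 1.572/0.608² = 4.25; five-month 0.750/0.417² = 4.32; ratio 0.98. Over shapes and course lengths the range is 0.90-0.99, so there is no gain.
- Effect only from course end: both windows hold five affected months. The past-year sum is 2 − 0.083 − 0.307 = 1.610 against 0.750, a ratio of 2.15. The range is 2.15-2.29.
- Effect from one month in: 1.19-1.34.

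So the better window depends on when the effect begins.

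**The case against.** The timing is unsettled. The protocol says "The schematic illustration is mentioned below in figure 4"; that figure is not in the text available to me and may decide whether end-line is per cohort or one common date. Under a common date the past-year window is nearly right. This stands, and it is why the point is conditional.

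The protocol also allows the tools to be changed after pre-testing and piloting. That leaves room for a different recall period, but those passages do not address recall and the scale description still gives past-year codes.

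Baseline adjustment softens the loss: "The study dataset will be a closed cohort", so each woman's earlier score can be a covariate. The ratios above already allow for this. Without adjustment the frequency ratios are 1.6-2.6 after course and 2.6-5.0 from start.

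The size can also be questioned. If the hypothesised 20% is absolute (40% to 20% over a fully exposed year), the past-year window after course needs 182-226 per arm, close to the planned 225 before clustering; from start it needs 406-418. And if recent acts are recalled better than distant ones, the dilution is smaller.

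The remedy carries a risk of its own. Trained couples have a landmark, the first session, that control couples lack. A question anchored on the training could place acts in time differently by arm and exchange harmless attenuation for differential error. The wording must therefore avoid it.

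A reader might infer that the past-year window favours one arm or raises the false-positive rate. It does neither, because randomisation balances the pre-start months in expectation. A reader might also infer that a five-month window should be ruled out because it gains nothing with immediate onset. The onset check shows that this reverses if the effect builds over the course, which is plausible for skills taught weekly.

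**Conclusion.** The point holds in conditional form. With per-cohort timing, 35-58% of the recalled year precedes the first session (4.24/12 to 7/12), and a 20% relative fall in frequency shows as about 8% or 12-13%. With one common late end-line it shows as about 17%, and little needs to change.

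The month counts follow from the protocol's own figures, given each timing reading. The displayed falls add even recall and immediate onset. The sample-size ratios (about 1.3-1.4 after course, 1.5-1.65 from start for frequency, more for any-act prevalence) also rest on an assumed event model, an illustrative 40% prevalence and a baseline taken just before start. Because codes 1-6 are grouped frequencies with an open top category, the frequency figures are approximate.

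The documents do not support reading this as a threat to validity, nor the claim that a shorter window would make the trial adequately powered for a 20% relative fall in violence. It is an inexpensive gain in precision on a primary outcome.

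**What to change.** 1. Reconcile the Executive Summary and the Operational Plan: state whether the five months run from course start or course end, and whether end-line is per cohort or one common date.
2. At end-line, replace the past-year period with one no longer than the time since the cluster's first session, using a matched date in control clusters and capped at 12 months. Choose between since-start and since-course-end according to when an effect is expected, and do not rule out the shorter window. With a common end-line, keep 12 months where 12 have elapsed and shorten only for later cohorts.
3. Word the period identically in all arms, as a fixed number of months or by a calendar or local event, and never by reference to the training.
4. Keep the past-year item at baseline as a covariate, and adapt codes 7 and 8 to the new period.

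Costs: fewer recorded events, no direct comparability with published past-year figures, no like-for-like change from baseline, cluster-specific dates for interviewers to manage, and a brief re-check of the translated wording.
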